5.2 Inclusion Criteria

Investigators will be expected to maintain a screening log of all potential study candidates that includes minimum key information about the potential candidate, date, and outcome of the screening process (e.g., enrolled into study, reason for ineligibility, or refused to participate). The following inclusion criteria must be met for each subject:

1. At least 18 years of age.
2. Hb < 11 g/dL (females) or <12 g/dL (males) at screening visit
3. Serum ferritin <100 ng/mL for subjects with underlying inflammatory disease (e.g. IBD, CKD or CHF, as determined by high sensitive C-reactive protein (hsCRP) levels above the normal range) otherwise serum ferritin \leq 14 ng/mL in subjects with no apparent underlying inflammatory disease (as determined by hsCRP levels within normal range) at the screening visit
4. TSAT <16% (any subject) at the screening visit.
5. Microcytic, hypochromic anaemia at the screening visit, defined as:
 - a. MCHC < 32%
 - b. MCV < 80 fL
 - c. MCH < 27 pg
6. Subjects with the ability to understand the requirements of the study and abide by the study restrictions, and who agree to return for the required assessments
7. Before any study-specific procedure is conducted, the appropriate written informed consent must be obtained.

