11.7.2 Secondary

The secondary efficacy endpoints for this study are as follows:

- Percentage of subjects achieving an increase in Hb ≥ 2 g/dL from baseline at Weeks 2, 4, 6 and 8.
- Change in Hb from baseline to Weeks 2, 4, 6 and 8.
- The percentage of subjects with TSAT $\geq 16\%$ and serum ferritin ≥ 100 ng/mL (for subjects with underlying inflammatory disease as determined by hsCRP levels above the normal range) or serum ferritin >14 ng/mL (in subjects with no apparent underlying inflammatory disease as determined by hsCRP levels within normal range at screening) at Weeks 2, 4, 6 and 8.
- Change in TSAT from baseline to Weeks 2, 4, 6 and 8.
- Change in serum ferritin from baseline to Weeks 2, 4, 6 and 8.

Appropriate summary descriptive statistics will be determined for all secondary endpoints at each visit for the FAS population using raw scores. Where appropriate,

methods for imputing missing values for both primary and secondary analyses will be described in the SAP. If any spurious data have been identified during the data review process they will be flagged and considered as missing in the analyses. All spurious and unused data will be included and identified in individual data listings. Missing data will be shown as missing in the listings. For continuous secondary endpoints, either analysis of variance or analysis of covariance models will be used and where necessary, the repeated measures procedure will be implemented. Where appropriate, terms for treatment, gender, age and respective baseline characteristics will be included. For non-continuous endpoints, more non-parametric methods will be used to make treatment comparisons, details of which will be fully specified in the SAP. Significance level is set at an alpha of 0.05 and no adjustment will be made for testing multiple secondary outcomes. Some significant findings are expected to occur by chance so undue consideration will not be given to any particular significant difference. Moreover, interpretation of the results will be based on patterns of differences and in conjunction with the results of the primary analyses.

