4.6.2 Secondary Efficacy Analysis

All secondary endpoints will be analysed on the FAS and the PPS. All statistical tests will be performed at a 5% level (2-sided).

Percentage of subjects achieving an increase in Hb $\geq 2\text{ g/dL}$ from baseline at Weeks 2, 4, 6 and 8. The difference in proportions between the FCM and Venofer groups from baseline at Weeks 2, 4, 6 and 8 and its two-sided 95% confidence intervals (CIs) will be computed using the Wilson score method with continuity correction described by Newcombe (1998).

Change in Hb from baseline to Weeks 2, 4, 6 and 8. Summary statistics will be presented at baseline, Weeks 2, 4, 6 and 8. Treatment comparisons for change in Hb from baseline will also be assessed using an analysis of MMRM model including treatment, haemoglobin baseline, site and visit as factors. Interaction between visit and treatment is also included in the model. The covariance structure to model the within-subject errors will be unstructured. The REML will be used. The Kenward-Roger method will be used to estimate the denominator degrees of freedom. Type III tests for the least-squares (LS) means will be used for the statistical comparison; the 95% CI will also be reported. Treatment group comparisons at each visits will be reported. If the unstructured covariance matrix results in a lack of convergence, the heterogeneous Toeplitz covariance structure, followed by the heterogeneous autoregressive covariance structure, followed by the compound symmetry will be used. This order is specified according to a decreasing number of covariance parameters in the structure.

The percentage of subjects with ID correction defined as TSAT $\geq 16\%$ and serum ferritin $\geq 100\text{ ng/mL}$ (for subjects with underlying inflammatory disease as determined by hsCRP levels above the normal range) or $> 14\text{ng/mL}$ (in subjects with no apparent underlying inflammatory disease as determined by hsCRP levels within normal range) at Weeks 2, 4, 6 and 8. The difference in proportions between the FCM and Venofer groups at Weeks 2, 4, 6 and 8 and its two-sided 95% confidence intervals (CIs) will be computed using the Wilson score method with continuity correction described by Newcombe

(1998). Treatment comparisons of subjects with ID correction variable will be assessed using a logistic regression analysis with treatment, baseline serum ferritin, baseline TSAT, and site in the model.

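### The logistic model for iron-deficiency correction leaves out the screening hsCRP group that sets each subject's ferritin threshold, so it gives up precision that could be had at no cost

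*SAP*

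**What the plan says.** SAP 4.6.2 defines success as TSAT of at least 16% together with a ferritin threshold that depends on inflammation. The threshold is 100 ng/mL or more "for subjects with underlying inflammatory disease as determined by hsCRP levels above the normal range", and above 14 ng/mL "in subjects with no apparent underlying inflammatory disease as determined by hsCRP levels within normal range". At Weeks 2, 4, 6 and 8 it plans a difference in proportions with a two-sided 95% Newcombe-Wilson interval. It then adds a treatment comparison by "logistic regression analysis with treatment, baseline serum ferritin, baseline TSAT, and site in the model".

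Protocol 11.7.2 ties the classification to one time point: "as determined by hsCRP levels within normal range at screening". SAP 2.6.2 and 4.6.2 drop the reference to screening.

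Protocol 5.2 applies the same split at entry: "Serum ferritin <100 ng/mL for subjects with underlying inflammatory disease", and otherwise no more than "14 ng/mL in subjects with no apparent underlying inflammatory disease (as determined by hsCRP levels within normal range) at the screening visit".

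Randomisation is blocked by centre only (SAP 2.5), so the design does not balance the hsCRP group either.

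**The concern.** The two thresholds differ about seven-fold (100/14 = 7.1). If the harder one lowers the success rate, as seems likely, hsCRP group will be among the strongest baseline predictors of this outcome. A logistic model without a strong predictor loses power for the treatment term. It also has no direct way to correct an arm that happens to receive more inflamed subjects.

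Baseline ferritin is an imperfect substitute. Because of the entry limits, a ferritin clearly above 14 ng/mL marks an inflamed subject, but an inflamed subject may also enter with a low value. One linear ferritin slope therefore picks up only part of the group difference.

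At stake is the efficiency of the model-based comparison for an endpoint that Protocol 2.3.2 uses to confirm that iron stores are replenished.

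**Working it through.** **Inputs from the documents.** The thresholds, entry limits and model terms are given above. The planned size reproduces: (1.960 + 0.842)² × 2 × 0.70 × 0.30 / 0.15² = 146.5, so 147 per arm; 147/0.80 = 183.75, so 184 per arm and 368 in all. The plan states no power or effect size for iron-deficiency correction.

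**Inputs assumed.** The documents give no share with raised hsCRP, no success rates by group and no treatment odds ratio for this endpoint.

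**Step 1. Power at 147 per arm.** There were 1,500 simulated trials per setting. Entry ferritin was uniform on 2-14 (normal hsCRP) or log-uniform on 4-100 (raised). The within-group effect was +0.3 log-odds per SD of ferritin, the treatment odds ratio was 2.2, and there was no site term. Success pairs are iron sucrose rates for normal/raised hsCRP. Cells show power (%) without the group, with it, and the gain in points.

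| Inflamed share | 85/40% | 80/30% | 90/60% |
|---|---|---|---|
| 10% | 57, 61 (+4) | 64, 71 (+7) | 45, 47 (+2) |
| 20% | 57, 64 (+7) | 65, 72 (+7) | 49, 54 (+5) |
| 35% | 67, 75 (+8) | 65, 75 (+10) | 59, 64 (+5) |

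**Step 2. Different assumptions.** A second simulation used 184 per arm, odds ratio 2.0, TSAT in the model, 10-50% inflamed, and lognormal ferritin (median 6 in normal hsCRP; 8 or 25 in raised).

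- Success 80/55%: gain of about 1-5 points.
- Success 80/30%: about 5-11 points.
- Success 90/20%: about 10-25 points.
- Success 80/30%, 30% inflamed, 12 sites as factors: 0.68 to 0.77, so the gain survives a site term.
- No difference between groups: 0.79 to 0.79 and 0.80 to 0.80 (20% and 50% inflamed), so the extra term costs nothing.
- Under no treatment effect, type I error was 0.052-0.056 for the SAP terms and 0.052-0.059 with the group added.

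**Step 3. Chance imbalance.** Across simulated trials, the estimated treatment log-odds ratio was regressed on the between-arm difference in inflamed share (20% inflamed, 85/40%, 147 per arm, no TSAT or site).

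- Slope with treatment only: -2.36.
- Slope after adding linear baseline ferritin: -1.86.
- Share of the dependence removed: (2.36 - 1.86)/2.36 = 21%. Over the nine settings of Step 1 it was roughly 15-20%.
- With the hsCRP group in the model, most or all of the dependence goes.

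With 20% inflamed and 147 per arm, one SD of chance imbalance is √(2 × 0.20 × 0.80/147) = 0.047. It moves the log-odds ratio by about 0.047 × 1.86 = 0.09 in the ferritin-adjusted model, against a true value of ln 2.2 = 0.79.

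**The case against.** Much of the case against this point stands.

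- **Role of the model.** The endpoint is secondary and has no power target. Protocol 11.7.2 makes no multiplicity adjustment and warns against reading much into any single significant result. The Newcombe-Wilson interval is planned for the same endpoint and visits and does not depend on the model.
- **Direction of the ferritin adjustment.** A reader might infer that baseline ferritin adjusts the wrong way, because its pooled slope can be negative while higher ferritin helps within each group. In the second simulation the slope was negative in 82-100% of runs when the inflamed median was 25, and in 18-36% when it was 8 with 80/55% success. The inference fails. Inflamed subjects tend to have higher baseline ferritin and face the harder threshold, so a negative slope is the right sign for correcting an imbalance in inflamed share. Step 3 shows the adjustment is incomplete, not reversed.
- **Odds ratio.** A reader might also infer bias, since the median odds ratio was 1.9-2.2 without the group and 2.2-2.3 with it. That is mainly non-collapsibility: the two models estimate different conditional odds ratios.
- **Protocol commitment.** The sentence "Where appropriate, terms for treatment, gender, age and respective baseline characteristics will be included" follows the one on continuous endpoints, and the protocol leaves methods for non-continuous endpoints to the SAP. The SAP breaks no promise here.
- **Size.** It rests wholly on assumptions.

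None of this gives a reason to leave the term out. The flag is needed to score the endpoint, and the term cost no power even where the groups did not differ.

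**Conclusion.** The omission is plain in SAP 4.6.2, and its consequence is lost precision. For 10-35% inflamed, iron sucrose success of 80-90% against 30-60%, an odds ratio of 2.2 and 147 per arm without a site term, the loss is about 2 to 10 power points. It is nil if success does not differ by hsCRP group, and it reached about 25 points under the most extreme contrast tried (90/20%). Baseline ferritin corrects only a minor part of a chance imbalance in the inflamed share.

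The documents do not support calling the comparison invalid. Randomisation protects the type I error, and neither the primary analysis nor the unadjusted interval is touched. This is a free improvement to a secondary model, best made before database lock so that the covariate is pre-specified.

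**What to change.** In SAP 4.6.2, add the screening hsCRP group (above or within the normal range) as a factor in the iron-deficiency-correction logistic model, for both FAS and PPS. Keep baseline ferritin, baseline TSAT and site.

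In SAP 2.6.2 and 4.6.2, state that the group is determined at screening, as Protocol 11.7.2 does. hsCRP is measured at every visit, so without this the threshold and the covariate could be taken from different samples, or from one drawn after treatment began.

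The cost is a few words of SAP text and one binary covariate. Eligibility already requires screening hsCRP, and the flag has to be derived to score the endpoint. The same edit can align Appendix 3, which labels the PPS table for this endpoint a logistic model and the FAS table a repeated measures model.

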4.3 Demographics and Baseline Subject Characteristics

Subject demographic and baseline characteristics data (sex, race, age, weight, and height) will be collected on the demographics CRF. The following baseline laboratory parameters Hb, TSAT, Serum ferritin, hsCRP will be collected on the laboratory CRF.

The demographics will be summarised and listed (demographic listing includes dates of informed consent).

Body mass index (BMI) will be calculated from weight and height as below

$$\text{BMI} = \text{weight(kg)} / [\text{height(m)}]^2$$

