Change in TSAT from baseline to Weeks 2, 4, 6 and 8. Summary statistics will be presented at baseline, Weeks 2, 4, 6 and 8. Treatment comparisons for Change in TSAT from baseline will also be assessed using an analysis of MMRM model including treatment, haemoglobin baseline, site and visit as factors. Interaction between visit and treatment is also included in the model. The covariance structure to model the within-subject errors will be unstructured. The REML will be used. The Kenward-Roger method will be used to estimate the denominator degrees of freedom. Type III tests for the least-squares (LS) means will be used for the statistical comparison; the 95% CI will also be reported. Treatment group comparisons at each visits will be reported. If the unstructured covariance matrix results in a lack of convergence, the heterogeneous Toeplitz covariance structure, followed by the heterogeneous autoregressive covariance structure, followed by the compound symmetry will be used. This order is specified according to a decreasing number of covariance parameters in the structure.

Change in serum ferritin from baseline to Weeks 2, 4, 6 and 8. Summary statistics will be presented at baseline, Weeks 2, 4, 6 and 8. Treatment comparisons for Change in serum ferritin from baseline will also be assessed using an analysis of MMRM model including treatment, haemoglobin baseline, site and visit as factors. Interaction between visit and treatment is also included in the model. The covariance structure to model the within-subject errors will be unstructured. The REML will be used. The Kenward-Roger method will be used to estimate the denominator degrees of freedom. Type III tests for the least-squares (LS) means will be used for the statistical comparison; the 95% CI will also be reported. Treatment group comparisons at each visits will be reported. If the unstructured covariance matrix results in a lack of convergence, the heterogeneous Toeplitz covariance structure, followed by the heterogeneous autoregressive covariance structure, followed by the compound symmetry will be used. This order is specified according to a decreasing number of covariance parameters in the structure.

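### The MMRMs for change in TSAT and change in ferritin adjust for baseline haemoglobin and leave out each marker's own baseline, which costs some precision in two secondary analyses

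*SAP*

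**What the plan says.** SAP 4.6.2 gives three repeated-measures models, all with a visit-by-treatment interaction.

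- **Haemoglobin:** "Treatment comparisons for change in Hb from baseline will also be assessed using an analysis of MMRM model including treatment, haemoglobin baseline", with site and visit. Here the covariate is the endpoint's own baseline.
- **TSAT:** "Change in TSAT from baseline will also be assessed using an analysis of MMRM model including treatment, haemoglobin baseline, site and visit as factors". Baseline TSAT is absent.
- **Ferritin:** "Treatment comparisons for Change in serum ferritin from baseline will also be assessed using an analysis of MMRM model including treatment, haemoglobin baseline", again with site and visit. Baseline ferritin is absent.

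For the binary endpoint built from the same two markers (iron deficiency correction), the same section specifies a "logistic regression analysis with treatment, baseline serum ferritin, baseline TSAT, and site in the model".

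For continuous secondary endpoints, Protocol 11.7.2 allows analysis of variance or of covariance and then says: "Where appropriate, terms for treatment, gender, age and respective baseline characteristics will be included".

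The values needed are available. SAP 4.3 states: "The following baseline laboratory parameters Hb, TSAT, Serum ferritin, hsCRP will be collected on the laboratory CRF".

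**The concern.** Three places in the documents suggest own-baseline adjustment: the protocol's covariate sentence, the haemoglobin model and the logistic model. The TSAT and ferritin paragraphs do otherwise and give no reason. As written, each marker is analysed as a change score. Its baseline is subtracted, but there is no regression adjustment for it.

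Two secondary comparisons are at stake. Iron parameters are named in a secondary objective (Protocol 3.2), and Protocol 2.4 lists ferritin and TSAT with haemoglobin as the measures by which treatment success is compared. Some chance imbalance is plausible. The ferritin entry limit is below 100 ng/mL with raised hsCRP and at most 14 ng/mL otherwise, so baseline ferritin mixes two ranges. SAP 2.5 describes blocking by centre and no stratification by inflammation or iron status.

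**Working it through.** **The plan's own figure.** The only design calculation concerns the primary endpoint. With 70% responders in both arms, a 15-point margin, one-sided 2.5% and 80% power:

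n = (1.960 + 0.842)² × 2 × 0.70 × 0.30 / 0.15² = 146.5, so 147 per group.

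Then 147/0.80 = 183.75, so 184 per group and 368 in total. This reproduces the plan, and the choice of TSAT and ferritin covariates plays no part in it. No SD, correlation or power is stated for either marker.

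**Inputs that must be assumed.** Let s0 and s1 be the SDs at baseline and at a follow-up visit, k = s0/s1, and r their correlation. The slope of follow-up on baseline is b = r/k. Baseline haemoglobin is taken to say little about baseline TSAT or ferritin.

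**Variance at a single visit.**

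- Change score without own baseline: s1²(1 + k² − 2rk)
- With own baseline as covariate: s1²(1 − r²)
- Difference: s1²(k − r)², so the proportional excess is (k − r)²/(1 − r²)

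The excess is never negative and is zero only when k = r.

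| k | r | Excess variance | CI wider by |
|---|---|---|---|
| 0.3 | 0 | 0.09/1 = 9% | 4.4% |
| 0.3 | 0.1 | 0.04/0.99 = 4% | 2.0% |
| 0.3 | 0.2 | 0.01/0.96 = 1% | 0.5% |
| 0.5 | 0 | 0.25/1 = 25% | 11.8% |
| 0.5 | 0.1 | 0.16/0.99 = 16% | 7.8% |
| 0.5 | 0.2 | 0.09/0.96 = 9% | 4.6% |

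Outside this range, k = 0.1 with r = 0 to 0.3 gives 0% to 4%. A small k does not guarantee a small loss: k = 0.1 with r = 0.5 gives 0.16/0.75 = 21%. At k = 1 with r = 0.1 to 0.5 the excess is 82% to 33%, but k near 1 would mean that the spread after treatment is no larger than the spread under the entry limits.

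**Shift for an observed imbalance.** Given a baseline difference d between arms, the change-score contrast moves by −(1 − b)d. At k = 0.5, r = 0.2, b = 0.4 and the shift is −0.6d. At k = r it is zero, and for b above 1 the sign reverses.

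**The two effects are one.** With n per arm, Var(d) = 2s0²/n. So the variance due to the shift is (1 − r/k)² × 2s0²/n = (k − r)² × 2s1²/n, which is exactly the excess variance above.

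**Simulation.** With 147 per arm, one visit and 3,000 replicates per setting, the mean error of the haemoglobin-adjusted contrast was about 0 throughout. At k = 0.5, r = 0.1 its variance was 1.18 times that of the own-baseline model (formula 1.16), and 1.15 times when baseline haemoglobin correlated 0.3 with the marker's baseline. Haemoglobin therefore recovered little. The slope on the imbalance was −0.82 (formula −0.80), against −0.03 with own-baseline adjustment.

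**How large d could be for TSAT.** Entry requires "TSAT <16% (any subject) at the screening visit". If baseline values stay between 0 and 16, the SD is at most 8 points, and a 1.96-standard-error imbalance with 147 per arm is at most 1.96 × 8 × √(2/147) = 1.8 points. For a uniform spread the SD is 16/√12 = 4.6 and the imbalance is 1.1 points. At b = 0.4 these move the estimate by 1.1 and about 0.6 points.

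**The case against.** The strongest reply is that nothing here is invalid. Randomisation makes the contrast unbiased on average, and its interval already reflects the larger variance. Listing chance imbalance and lost precision as separate harms would count one effect twice. That stands. What remains is conditional: once an imbalance has been seen, the planned estimate carries part of it and the own-baseline estimate essentially does not.

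A reader might infer that the SAP breaches the protocol. The documents do not support that. Protocol 11.7.2 permits analysis of variance, and its covariate sentence is conditional. The same sentence names gender and age, which all three MMRMs omit. This is an unexplained departure from what the protocol indicates.

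A reader might also infer that any baseline difference passes in full into the treatment estimate. That would need b = 0.

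A copying slip from the haemoglobin paragraph is likely but is inference. Baseline haemoglobin has a case as a covariate, because screening haemoglobin drives the planned iron dose in both arms (Protocol 7.2.1 and 7.2.2). That is a reason to keep it and does not justify leaving out the marker's own baseline.

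Finally, the entry limits on TSAT and ferritin may make baseline spread small beside the spread after repletion, and both markers are summarised at baseline, so an imbalance would be visible. Both points lower the stakes. Neither supplies the missing covariate.

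**Conclusion.** The point holds as a matter of efficiency and consistency, at moderate to low severity. The text is unambiguous for both markers, and no other section supplies the own baseline or a reason for omitting it. The direction of the effect is certain in large samples: leaving out the own baseline cannot improve precision.

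The size cannot be determined from the documents. Under the assumed k of 0.3 to 0.5 and r of 0 to 0.2, the variance is about 1% to 25% larger and the interval about 0.5% to 12% wider. If k and r are both small, the loss is a few percent or less. These figures are for one visit and are an approximation for a four-visit MMRM.

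Two larger conclusions are tempting. One is that the TSAT and ferritin results would be biased; on average they would not be. The other is that the trial's main conclusion is at risk. The primary non-inferiority test compares haemoglobin responder proportions without these models, and the sample size does not depend on them. Protocol 11.7.2 also makes no multiplicity adjustment across secondary outcomes and cautions against giving weight to any single significant one.

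**What to change.** In SAP 4.6.2, enter baseline TSAT as a continuous covariate in the TSAT model and baseline ferritin as a continuous covariate in the ferritin model. Baseline haemoglobin may be kept as an additional covariate in both. State that these baselines are continuous, since the present wording lists baseline haemoglobin among the factors.

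The cost is a few words in each of two paragraphs. Both baselines are already collected, and the sample size does not change. Make the edit before database lock: Protocol 11.1 requires the SAP to be final by then and any later deviation to be explained in the study report, and a covariate change made after results are seen could look data-driven.
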